2.3 Correlative and Exploratory

2.31 To evaluate fatigue, and other patient-reported outcomes.
2.32 To evaluate clinical features, treatment technique, dose-volume parameters, histologic and genetic variants associated with fair and poor cosmetic outcomes or unplanned surgical intervention.
2.32 To evaluate the costs and comparative effectiveness of treatment
2.33 Compare the use of photon therapy with spot scanning proton therapy in two different hypo-fractionated whole breast schemas.

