2.88 (0.75–5.01) Gy; $a = 0.08 \pm 0.02 \text{ Gy}^{-1}$; potential doubling time $T_d = 14.4 \pm 7.8$ day.⁴³ The fractionation regimens in table 1 (modified from Qi et al.)⁴³ is based on the fitting of clinical data including the hypofractionated randomized trials mentioned above and justifies the five fraction regimen proposed for arm 2. The concurrent boost dose of 6 Gy x 5 is also based in part on the work of Formenti et al. who recently reported the 5-year results of a prospective trial of 3D-CRT APBI of 100 patients treated in the prone position to a total dose of 30Gy in 6Gy fractions. At a median follow-up of 64 months, there has been just one local recurrence and one contralateral recurrence and cosmesis was rated as good/excellent in 89% of patients with at least 36 months follow-up.⁵³ Livi et al has also shown excellent 5-year toxicity, cosmetic outcome and local failure results employing a dose of 30Gy in 5 treatments.⁵⁴ The control arm for this study will be 15 fractions based on the favorable long term follow-up of the UK START B⁵⁵. More recently the initial toxicity results of the fast forward trial have been published. Very low rates of grade 3 toxicity were seen using either the 40 Gy over 3 weeks, or 26 Gy or 27 Gy over one week.⁵⁶ It is possible that the spot proton RBE may be different than 1.1 for hypo-fractionated treatments. Trials like the currently proposed would be critical to define differences in RBE with spot scanned hypofractionated radiation as well as the cancer and normal tissue alpha/beta.

Table 1

Arms	Tx	Tumor dose 2Gy
50Gy in 2Gy	25	50Gy
45Gy in 2.26Gy	20	50Gy
33.4Gy in 3.34Gy	10	50Gy
24.7Gy in 4.98Gy	5	50Gy

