5.0 Stratification Factors

- 5.1 Treatment modality: Photons vs. spot scanned proton therapy. Of the total 110 patients in this study, fifty-five would be treated in each arm. We will

allow a maximum of 28 patients per arm per treatment modality (photons/x-ray or protons).

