7.0 Protocol Treatment

Doses throughout will be prescribed in Gy (RBE) / Gy or Gy. One Gy will be the equivalent of one Gy (RBE) / Gy for proton therapy for the purposes of the descriptions below. Radiation therapy must begin within 12 weeks of the last breast cancer surgery or the last dose of adjuvant chemotherapy and no sooner than 14 days since the last chemotherapy. The dose, schedule, and timing (neoadjuvant vs adjuvant) of chemotherapy and endocrine therapy are at the discretion of the treating oncologists. Concurrent cytotoxic chemotherapy with radiotherapy is not allowed. Use of anti-HER2 therapy during radiotherapy is permitted.

The treatment technique (photon/x-ray vs. proton) utilized will be at the physician's discretion and will be based on technical considerations, availability at the radiation oncology facility, insurance coverage considerations, and patient preference. See section 7.4.

7.1 Radiation Therapy, Arm 1

Patients who had breast conserving surgery and are randomized to arm 1 (standard fractionation) will receive whole breast radiotherapy delivered to the breast CTV with or without a sequential boost to the lumpectomy cavity CTV. Boost indications will be left to physician discretion. Potential risk factors suggesting increased absolute benefit from a boost include but are not limited to age < 40, close margins, extensive DCIS adjacent to the invasive tumor.^{58,59}

7.2 Radiation Therapy, Arm 2

Patients who had breast conserving surgery and are randomized to arm 2 (5 fraction hypofractionation) will receive whole breast radiotherapy in 5 daily fractions delivered to the breast CTV with or without a concurrent boost to the lumpectomy cavity CTV. Boost indications will be left to physician discretion. Potential risk factors suggesting increased absolute benefit from a boost include but are not limited to age < 40, close margins, extensive DCIS adjacent to the invasive tumor.^{58,59}

7.3

Dose Specifications

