16.6 Analysis Plan

The analysis for this trial will commence at the planned time points and at the time the patients have become evaluable for the primary endpoint.

16.6.1 Primary Analysis: The primary analysis will be to estimate the difference in the complication rate (adverse cosmesis and grade 3+ toxicities) which is defined as the 24-month complication rate in experimental arm minus that in the control arm. All patients meeting the eligibility criteria who have signed a consent form and started treatment will be in the primary analysis. The complication rate will include all women evaluable at 24 months. Those who have recurrent disease or die before 24 months will not be included in this calculation. We expect that <3% of patients will not be found eligible based on failure or death.²⁴ The complication rate will be estimated using a binomial estimator in both experimental arm

and control arm, and a one-sided 90% confidence interval of the difference will be computed with normal approximation. As mentioned above, the following decisions will be made based on the 90% CI:

- ***The upper bound of the 1-sided 90% CI of the difference lies below 15%:*** The experimental arm regimen is acceptable.
- ***The upper bound of the 1-sided 90% CI of the difference lies above 15%:*** The experimental arm regimen is unacceptable.

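### Allocation is stratified by modality, but the primary 5- versus 15-fraction difference is unstratified, and exploratory objective 2.33 contrasts a factor that is not randomised

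*Combined protocol and SAP*

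**What the plan says.** Section 5.0 names one stratification factor: "Treatment modality: Photons vs. spot scanned proton therapy". It adds: "Of the total 110 patients in this study, fifty-five would be treated in each arm", with at most 28 patients per arm in either modality. Section 6.2 feeds this factor, together with the registering membership, into a Pocock-Simon dynamic allocation to the fractionation arms.

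Modality itself is not allocated. Section 7.0 leaves it to the physician's "discretion and will be based on technical considerations, availability at the radiation oncology facility, insurance coverage considerations, and patient preference".

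Section 16.6.1 defines the primary analysis: "The complication rate will be estimated using a binomial estimator in both experimental arm" and in the control arm, then a one-sided 90% confidence interval for the difference by normal approximation, judged against a 15-point margin. The secondary and exploratory analyses in 16.6 are by treatment arm or between arms. The only subset examination mentioned is by racial grouping (16.92).

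Objective 2.33, listed as correlative and exploratory, is to "Compare the use of photon therapy with spot scanning proton therapy in two different hypo-fractionated whole breast schemas". Section 16 gives it no endpoint, model or adjustment set. Section 1.4 says of protons: "It is possible that the spot proton RBE may be different than 1.1 for hypo-fractionated treatments".

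**The concern.** Two things do not line up.

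First, a factor important enough to stratify and cap is dropped at the analysis stage. An analysis that conditions on the allocation factor is the usual counterpart of stratified allocation. Without it, the standard error ignores the balance that the design created. The randomised comparison of 5 with 15 fractions inside each modality, which the design keeps nearly balanced, is also never displayed.

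Second, the one objective that does concern modality compares groups formed by clinical choice. Technical suitability, access, insurance and preference may relate to cosmesis or toxicity. The two modalities are also planned to different limits (section 7.9: breast-skin maximum, goal/major violation, 105%/110% for protons and 107%/115% for photons). A crude contrast would mix the beam with patient selection and planning limits.

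At stake are a small loss of precision, a by-modality split that would look post hoc if first made after the results are known, and a photon-proton figure that could be read as a treatment effect.

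**Working it through.** **Inputs.** From the plan: 50 evaluable per arm (16.4), 10% complications in the control arm (16.4), margin 15 points, one-sided alpha 0.05 and 80% power (16.5), one-sided 90% bound (16.5, 16.6.1). Derived, not stated: about 25 evaluable per arm per modality, because 55 per arm with a cap of 28 leaves 27 or 28 per cell before losses. Assumed: the modality-specific complication rates below.

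**1. The plan's own figure.** SE = √(2 × 0.10 × 0.90 / 50) = 0.060. Power = Φ(0.15/0.060 − 1.645) = 80.4%, so the stated 80% is reproduced for the comparison pooled over modality. At the level of the one-sided 90% bound (z = 1.2816) the same formula gives 88.8%. That mismatch of levels is a separate matter.

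**2. Stratifying the primary difference.** With equal cells, the Mantel-Haenszel risk difference is the average of the two within-modality differences. With rates p₁ and p₂ in the two modalities, the same in both arms:

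SE = √{¼ × [2p₁(1 − p₁)/25 + 2p₂(1 − p₂)/25]}

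| Assumed modality rates | Stratified SE | Ratio to 0.0600 |
|---|---|---|
| 10% / 10% | 0.0600 | 1.000 |
| 8% / 12% | 0.0599 | 0.998 |
| 5% / 15% | 0.0592 | 0.986 |
| 3% / 17% | 0.0583 | 0.972 |

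Stratifying therefore costs nothing here and shortens the SE by about 0.2% to 3%.

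**3. Within one modality (25 per arm, 10% in both arms).** SE = √(2 × 0.09 / 25) = 0.0849. The upper bound lies 1.2816 × 0.0849 = 10.9 points above the estimate, against 7.7 points pooled. Exact enumeration of the plan's rule gives a bound below 15 points with probability 0.741. With no true excess, each bound therefore exceeds 15 points 1 − 0.741 = 26% of the time, and at least one of the two does so in 1 − 0.741² = 45% of trials.

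**4. Arm-by-modality difference.** SE = √(4 × 0.09 / 25) = 0.12, so the 95% half-width is 1.96 × 0.12 = 23.5 points.

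**5. Photon versus proton, as in 2.33.** The 95% half-width is 1.96 × √(2 × 0.09 / 50) = 11.8 points overall and 1.96 × √(2 × 0.09 / 25) = 16.6 points within one schedule, before any confounding.

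**6. An excess confined to one modality.** Suppose 10% everywhere except Arm 2 protons. The table gives exact acceptance probabilities under the plan's rule.

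| Arm 2 protons | True pooled difference | Pooled rule | Stratified rule |
|---|---|---|---|
| 10% | 0 points | 0.891 | – |
| 25% | 7.5 points | 0.435 | 0.449 |
| 30% | 10 points | 0.286 | 0.303 |

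A uniform 17.5% in Arm 2, also a 7.5-point difference, is accepted with probability 0.437. The 43% is what the rule does at 7.5 points, wherever the excess sits, and stratifying raises it slightly.

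**The case against.** Several arguments on the other side are sound.

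- **The fractionation question is analysed.** A reader might infer that the stratified design's question goes unanswered. It does not: 5 versus 15 fractions is the primary analysis, randomised and balanced on modality. Only the stratified and within-modality forms are absent.
- **Objective 2.33 is one exploratory line.** It claims no causal inference and carries no test or decision. A non-randomised exploratory comparison is not an error in itself, and section 2.3 already lists treatment technique among features to relate to cosmesis. Labelling is enough; replacement is not called for.
- **The 43% and 29% acceptance figures are not a fault that stratification corrects.** They may look like a failure of the pooled analysis. They are ordinary behaviour at true differences of 7.5 and 10 points, and stratifying does not lower them.
- **The evidence for a modality-specific fractionation effect is thin.** The RBE sentence in 1.4 speaks of hypofractionated treatment, and 2.33 describes both schedules in that way, so it does not single out the 5-fraction arm. The differing skin limits apply to both arms within a modality.
- **Subgroup rows invite misreading.** The 45% figure shows this. For a 15-point discordance the interaction has only about 20% power (two-sided 0.05, SE √[(0.1875 + 3 × 0.09)/25] = 13.5 points).

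These points limit the concern. They do not explain why the allocation factor is left out of the analysis, and stratifying the estimate has no offsetting cost.

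**Conclusion.** The point holds in a limited form. Modality is used to allocate patients but nowhere in section 16, and objective 2.33 sets up a contrast that randomisation does not protect and that has no stated method. The primary comparison remains valid. An acceptable result under 16.5 recommends further investigation rather than adoption, which also limits the harm.

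The benefit of stratifying is consistency with the design plus a 0.2% to 3% shorter standard error. That range rests on assumed modality rates and about 25 evaluable per cell, neither of which the plan states. Within-modality estimates are too imprecise to carry a decision. It would be equally wrong to say that they could never meet the margin: 10.9 points is below 15, and with equal 10% rates the bound falls under the margin 74% of the time. They are useful as description only.

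**What to change.** 1. **Section 16.6.1:** estimate the primary difference stratified by modality, for example as a Mantel-Haenszel risk difference, with the same one-sided bound and the same 15-point margin.
2. **Section 16.6, descriptive rows:** report the 5- versus 15-fraction difference in 24-month complications with a confidence interval within each modality, and the arm-by-modality difference. State that no decision rule applies. State also that, with no true excess and about 25 evaluable per cell, each one-sided 90% bound would exceed 15 points about 26% of the time (at least one modality in about 45% of trials).
3. **Objective 2.33:** keep it, and label any photon-proton comparison non-randomised and descriptive. If an adjusted comparison is wanted, name the covariates in advance.

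The cost is a few sentences of analysis text and a few table rows. Modality is already recorded before allocation, so no new data are needed, and sample size, margin, visits and treatment are unchanged. The main drawback is the risk that the wide within-modality intervals are over-read, so the warning in item 2 should stand beside the table. The changes should be made before outcome data are examined.

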3.0 Patient Eligibility

3.1 Inclusion Criteria

3.12 Age \geq 18 years.
3.13 Histological confirmation of breast cancer.
3.14 Pathologic Stage T0-T3N0-N1M0. (8th edition)
3.15 ECOG Performance Status (PS) 0 to 2. (Appendix I).
3.16 Able to and provides IRB approved study specific written informed consent.
3.17a Study entry (randomization) must be within 12 weeks of last surgery (breast or axilla) or last chemotherapy (if applicable).

- 3.17b Willing to return to enrolling institution for follow-up (during the active monitoring phase of the study).
- 3.18 Fair, good or excellent cosmesis, as determined by trained nurse assessment using the Harvard Cosmetic Scale.
- 3.19 Radiotherapy must begin within 12 weeks of the last breast cancer surgery or the last dose of adjuvant chemotherapy.
- 3.20 Breast conserving surgery and indications for whole breast radiotherapy.

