6.2 Randomization Procedures

6.21 The factors defined in Section 5.0, together with the registering membership, will be used as stratification factors.

6.22 After the patient has been registered into the study, the values of the stratification factors will be recorded, and the patient will be assigned to one of the following treatment groups using the Pocock and Simon dynamic allocation procedure which balances the marginal distributions of the stratification factors between the treatment groups.⁵⁷

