7.9.1.1.1 Per protocol \geq D95% will receive \geq 95% of prescription;
Variation acceptable \geq D90% receives \geq 90% of prescription

7.912 Tumor CTV

7.9.1.2.1 Per protocol D95% receives \geq 95% of dose; variation acceptable D90% receives \geq 90% of the boost dose

7.913 Robustness analysis **for Protons**

7.9.1.3.1 Breast CTV coverage would be evaluated for 5mm movements or 3% range changes. Per protocol Breast CTV V90% receives \geq 95% of the prescription dose; variation acceptable \geq V90% receives \geq 90% of the prescription dose.

7.9.1.3.2 Under the same robustness evaluation criteria, plans will be evaluated for D max. Variation acceptable D0.01cc % \leq 120%

Protons DVH summary table

		Goal	Major violation ¹
Breast CTV		\geq V95% will receive \geq 95% of prescription	V90% $<$ 90% of prescription
		Dmax $<$ 107%	Dmax $>$ 115%
Tumor Bed CTV		\geq V95% will receive \geq 95% of prescription	V90% $<$ 90% of prescription
		Dmax $<$ 107%	Dmax $>$ 115%
Breast CTV robustness		V90% $>$ 90% of prescription	V90% $<$ 90% of prescription
Heart	Max dose	\leq 25% of prescription	$>$ 33% of prescription
	Mean	$<$ 0.1Gy	$>$ 1Gy
Breast Skin	Max dose	\leq 105% of prescription	$>$ 110% of prescription
Lung Ipsilateral	V50% of prescription	\leq 10%	$>$ 15%
	V20	record	
Lung contralateral	V50%	\leq 7%	$>$ 10%
Lung Total	Mean dose	record	
	V20Gy	record	
	V50%	record	
LAD (optional)	Mean dose	record	
	Max dose	record	
RCA (optional)	Mean dose	record	
	Max dose	record	

1. Major violations do not exclude patients from the protocol as it is an intent to treat analysis

Photons (x-rays) DVH summary table

		Goal	Major violation
PTV Eval		\geq V95% will receive \geq 95% of prescription	V90% <90% of prescription
		Dmax <107%	Dmax >115%
Tumor Bed CTV		\geq V95% will receive \geq 95% of prescription	V90% <90% of prescription
		Dmax <107%	Dmax >115%
Breast CTV robustness		V90% >90% of prescription	V90% <90% of prescription
Heart	Max dose	\leq 33% of prescription	>50% of prescription
	Mean	<1Gy	>2Gy
Breast Skin	Max dose	\leq 107% of prescription	>115% of prescription
Lung Ipsilateral	V50% of prescription	\leq 10%	>15%
	V20	record	
Lung contralateral	V50%	\leq 7%	>10%
Lung Total	Mean dose	record	
	V20Gy	record	
	V50%	record	
LAD (optional)	Mean dose	record	
	Max dose	record	
RCA (optional)	Mean dose	record	
	Max dose	record	

1. Major violations do not exclude patients from the protocol as it is an intent to treat analysis

Quality Assurance Documentation

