13.0 Treatment/Follow-up Decision at Evaluation of Patient

Follow-up data will be collected and entered after the observation phase outlined in section 4.0. If the patient is still alive after 5 years have elapsed from the on-study date, no further follow-up is required by this protocol.

- 13.1 Patients who have a recurrence while receiving therapy or during observation will go to the event-monitoring phase and be followed
- 13.2 Patients who discontinue treatment or observation for reasons other than recurrence will go to the event-monitoring phase and be followed
- 13.3 Patients who will not receive any radiation treatment or who will receive radiation treatment elsewhere will move to event monitoring phase.
- 13.4 A patient is deemed *ineligible* if after registration, it is determined that at the time of registration, the patient did not satisfy each and every eligibility criteria for study entry. The patient may continue treatment off-protocol at the discretion of the physician as long as there are no safety concerns, and the patient was properly registered. The patient will go directly to the event-monitoring phase of the study (or off study, if applicable).

If the patient received treatment, all data up until the point of confirmation of ineligibility must be submitted. Event monitoring will be required per Section 18.0 of the protocol.

If the patient never received treatment, on-study material and the End of Active Treatment/Cancel Notification Form must be submitted. No further data submission is necessary.

- 13.5 A patient is deemed *withdrawn* if she is removed from the study for any reason before any study treatment is given. On-study material and the End of Active Treatment/Cancel Notification Form must be submitted. No further data submission is necessary.

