16.0 Statistical Considerations and Methodology

- 16.1 Overview: This is an open label phase III randomized controlled trial to determine the safety of 5 fraction vs 15 fraction radiotherapy after breast conserving surgery. The goal is to determine whether the difference in 24-month complication rates between the experimental arm and the control arm is acceptable. Of interest is whether the experimental arm results in an unacceptable increase in the 24-month complication rate. If it does not, then the experimental arm will be recommended for further study. If the 24-month complication rate is found to be unacceptable, then the recommendation would be to do no further studies of the experimental arm.

- 16.2 Primary and Secondary Endpoints

16.21 Primary Endpoint: The 24-month complication rate, defined as the percentage of women evaluable at 24 months who develop one or more of the following events:

- 1) grade 3 or higher late adverse event OR
- 2) deterioration of cosmesis from excellent/good to fair/poor or from fair to poor at the 24-month evaluation (using the Harvard/NSABP/RTOG Cosmesis Scale)

16.22 Secondary Endpoints:

16.221 Acute and late adverse events including grade ≥ 2 pneumonitis.

16.223 Locoregional control, invasive disease-free, distant recurrence, disease-free survival, cause-specific survival, overall survival.

The following definitions are used for the secondary endpoints of interest:

- *Acute adverse events*: any adverse event, regardless of attribution, that occurs in the first 90 days post-RT.
- *Late adverse events* (up to 5 years post RT): any adverse event that occurred after the first 90 days post-RT and up to 5 years post-RT.
- *Ipsilateral breast tumor recurrence (IBTR)*: this is defined as local recurrence from trial registration as a first event at 5 years. IBTR is defined as both invasive and non-invasive breast cancer involving the same breast parenchyma as the original tumor.
- *Regional recurrence*: invasive breast cancer in the axilla, regional lymph nodes, chest wall, and skin of the ipsilateral breast at 5 years.
- *Distant recurrence*: metastatic cancer that has either been biopsy confirmed or clinically diagnosed as recurrent invasive breast cancer at 5 years.

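### Criterion 3.19 makes a post-randomisation event (radiotherapy starting within 12 weeks) an eligibility condition, so a treated late starter could be removed from the primary analysis after her arm is known.

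*Combined protocol and SAP*

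**What the plan says.** - **Section 3.1, criterion 3.19**, in the inclusion list: "Radiotherapy must begin within 12 weeks of the last breast cancer surgery or the last dose of adjuvant chemotherapy".
- **Section 3.1, criterion 3.17a**: "Study entry (randomization) must be within 12 weeks of last surgery (breast or axilla) or last chemotherapy (if applicable".
- **Section 7.0** gives the start limit again, as a treatment requirement: "Radiation therapy must begin within 12 weeks of the last breast cancer surgery or the last dose of adjuvant chemotherapy".
- **Section 6.1** registers a woman once she has consented and met the eligibility criteria. **Section 6.22** places arm assignment after that: "After the patient has been registered into the study, the values of the stratification factors will be recorded", and only then is she allocated.
- **Section 16.1** describes the design: "This is an open label phase III randomized controlled trial".
- **Section 16.6.1** defines the primary analysis set: "All patients meeting the eligibility criteria who have signed a consent form and started treatment will be in the primary analysis".
- **Section 13.4** sets this test for calling a woman ineligible later on: "it is determined that at the time of registration, the patient did not satisfy each and every eligibility criteria for study entry". Such a patient goes to event monitoring or off study.
- **Section 18.1**: in the table of forms, only the Patient Status Form is marked for event monitoring. The Patient Assessment form is marked for end of treatment and observation only.
- **Section 7.9**, footnote to the DVH tables: "Major violations do not exclude patients from the protocol as it is an intent to treat analysis".

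**The concern.** An eligibility criterion should be decidable before allocation. Criterion 3.19 is settled only on the day radiotherapy begins, when patient, physician and study team all know the arm. If failing it makes a woman ineligible, the primary analysis set depends on something that happens after randomisation.

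What is at stake is mainly selection. The endpoint is a difference in 24-month complication rates with about 50 women per arm, so removing a few women from one arm can shift that difference if their risk is not typical. The loss might also be beyond repair at the analysis stage, because a woman moved to event monitoring may have no 24-month cosmesis score to put back.

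**Working it through.** **1. Can 3.19 be checked at registration?** Twelve weeks is 84 days. A woman randomised on day d has 84 − d days left to start:

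| Randomised on day | Days left to start |
|---|---|
| 56 | 28 |
| 70 | 14 |
| 77 | 7 |
| 84 | 0 |

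All four satisfy 3.17a. For none of them is 3.19 a known fact at registration. The two clocks also differ slightly: 3.17a counts from breast or axillary surgery, or from the last chemotherapy; 3.19 counts from breast cancer surgery or the last adjuvant chemotherapy.

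**2. Does failing 3.19 lead to exclusion?** Set side by side, the passages allow two readings.
- Literal: a late starter did not meet 3.19, so she is outside the 16.6.1 set and goes to event monitoring.
- Eligibility fixed at registration (6.1, 13.4): a later slip does not count, so she stays. But nobody has begun radiotherapy at registration, so this works only if 3.19 means a planned start, which no section says.

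**3. The plan's own figure.** Inputs from 16.5: 10% in both arms, margin 15%, 50 per arm, one-sided alpha 0.05.

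SE = √(2 × 0.10 × 0.90 / 50) = 0.060. Power = Φ(0.15/0.060 − 1.645) = Φ(0.855) = 80.4%.

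The stated 80% is reproduced. With the one-sided 90% bound that 16.6.1 specifies, power is Φ(2.5 − 1.282) = 88.8%. Because the two sections use different levels, results below are given for both.

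**4. Effect of removing late starters.** The acceptance rule is p̂E − p̂C + z√[p̂E(1 − p̂E)/nE + p̂C(1 − p̂C)/nC] < 0.15. Its probability was found by enumerating both binomial distributions. True rates are 25% experimental and 10% control, the null hypothesis in 16.5. Suppose k of 50 experimental-arm women are removed and their risk is r; the rate among those left is (12.5 − k·r)/(50 − k). Both k and r are assumptions.

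| Removed from experimental arm | Rate among those left | False acceptance, 90% bound | False acceptance, 95% bound |
|---|---|---|---|
| None | 25.0% | 10.5% | 5.8% |
| 3, average risk (25%) | 25.0% | 10.9% | 5.8% |
| 3, risk 50% | 11.0/47 = 23.4% | 15.4% | 8.7% |
| 5, average risk (25%) | 25.0% | 10.6% | 5.7% |
| 5, risk 50% | 10.0/45 = 22.2% | 18.8% | 11.3% |

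The bias can also run the other way. If 3 control-arm women at 50% risk are removed instead, the control rate among those left is (5 − 1.5)/47 = 7.4%. False acceptance with the 90% bound then falls from 10.5% to 5.9%. When both true rates are 10%, correct acceptance falls from 89.1% to 81.9%.

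**5. Loss of numbers.** Removing an assumed 2%, 5% or 10% from 50 per arm takes the 80.4% power (alpha 0.05) to 79.7%, 78.6% or 76.6%. This is a modest loss.

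**The case against.** The strongest reply is section 13.4. It ties ineligibility to the time of registration, and section 6.1 closes eligibility at the same point. On a fully literal reading of 3.19 nobody could be registered at all, so the workable meaning is a planned start, and a woman whose start slips remains eligible. This stands as a reason to call exclusion possible rather than certain. It does not settle the matter, because no section says that 3.19 means a planned start, and the people left to decide would know the arm.

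Other points that stand:
- A reader might infer from section 7.0 that availability and insurance make start time depend on arm. The documents do not support that. Those factors govern the choice of photons or protons, which is a stratification factor recorded before allocation. Nothing in the documents links start date to fractionation arm, or delay to worse cosmesis.
- A reader might infer that one woman can change the verdict. Against 5/50 in control, 8/50 gives a 90% upper bound of 14.6%, and restoring one excluded woman with an event (9/51) gives 16.4%. But 8/50 is the last accepting count, chosen for that reason. Any binary comparison of this size flips there.
- The intent-to-treat footnote concerns dose-volume violations only. It gives no rule for 3.19, and its spirit favours keeping late starters.
- Section 16.4 adds 10 women for ineligibility and other losses. That covers numbers, not selection.
- No section says that simulation or planning must wait for randomisation, so a late randomisation need not mean a late start.

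**Conclusion.** The point holds as a gap in the rules, not as a demonstrated bias. Criterion 3.19 cannot be verified when eligibility is declared, and 16.6.1 makes eligibility a condition of entering the primary analysis. Section 13.4 leaves open how the two fit together. A treated late starter could therefore be removed, with knowledge of her arm, and lose her 24-month assessment. It would go too far to say that every late start removes a woman from the analysis.

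The size cannot be fixed from the documents, which give no late-start rate. With average risk among late starters, the chance of a wrong decision is essentially unchanged. The rise from 10.5% to 15.4% (90% bound), or from 5.8% to 8.7% (95% bound), rests on two assumptions: three removals, all from the experimental arm, and a 50% complication risk in those women. The change is worth making because it closes a route to post-randomisation exclusion at almost no cost.

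**What to change.** - Take 3.19 out of the inclusion criteria. Leave the start limit in section 7.0 unchanged, as a treatment requirement. No clinical time limit is altered.
- State in 13.4 and 16.6.1 that eligibility is fixed at registration. State also that a start later than 7.0 allows is a protocol deviation, and that the woman stays in her randomised arm, in the primary analysis and on the 24-month assessment schedule.
- Report late starts by arm.

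No new entry condition, such as a start date booked before randomisation, is needed; it would turn some women away without improving the comparison. The cost is amendment wording. The one downside is that a few women treated outside the start window remain in the analysis, and the by-arm report makes this visible.
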